## Introduction:

Endocuff Vision ( Olympus) is a disposable device that has 8 independently moving soft flexible arms arranged in a single row. The device comes in several sizes and can fit the tips of most commonly used colonoscopes. During intubation, the arms fall flat to the body of the scope as not to impede forward motion. Endocuff Vision is an FDA approved device that fits over the end of a colonoscope and has flexible soft fingers that project from the sides. These fingers can be used to pull back the folds in the colon and expose mucosa on the proximal sides. A number of studies indicate that Endocuff improves the adenoma detection rate (ADR) during colonoscopy. In a non-randomized retrospective evaluation, Endocuff resulted in better detection, faster insertion, and faster inspection (1).

Our aim in this study is to show in a prospective randomized trial Endocuff Vision could improve insertion because during loop withdrawal the cuff tends to stabilize the position of the tip, preventing its backward movement and speeding loop removal. Similarly, during inspection, the main goal is to evaluate the proximal sides of folds and flexures. The process is made easier and quicker by the device. Third, during polypectomy, Endocuff Vision helps to stabilize the position and the scope tip.

## Methods:

This will be a prospective, randomized controlled study. Subjects referred for screening or surveillance colonoscopy will be prospectively enrolled. They will be randomized to one of two arms, i.e High Definition colonoscopy or High Definition colonoscopy with Endocuff Vision.

A member of the research team will approach a potential subject to discuss participation in the study, including background of the proposed study, inclusion and exclusion criteria, benefits and risks of the procedures and follow-up. If this is of interest to the subject, the informed consent form is discussed and presented. The subject must sign the consent form prior to enrollment. This form will have prior approval of the study site's Institutional Review Board (IRB). Failure to obtain informed consent renders the subject ineligible for the study

## **Objectives:**

*Primary objectives* of the study are:

- To compare the insertion time, inspection time, the total time per polypectomy, and the total procedure time during High Definition colonoscopy with Endocuff Vision versus standard High Definition colonoscopy.

*Secondary objectives:*

- To compare the number of adenomas detected per subject with High Definition Endocuff Vision compared to Standard High Definition colonoscopy.
- To compare the detection rates for polyp subtypes (including advanced adenomas, serrated polyps, right sided adenomas, etc) for High Definition Endocuff Vision compared to Standard High Definition colonoscopy.

## **Primary End-point:**

- The inspection time will be shorter because the proximal sides of the folds are more quickly exposed with Endocuff Vision compared to standard colonoscope alone because of the ability of the Endocuff Vision to stabilize the position of the colonoscope tip during loop withdrawal, thus preventing its backward movement and speeding loop removal.

## **Criteria:**

All colonoscopies in the study will be performed by a qualified professional. Patients will be 40 and older and will be randomized to receive colonoscopy with or without the Endocuff. Data collected will include the type of scope used (adult versus pediatric), age, gender, indication, history of prior abdominal surgery and type, identification of diverticulosis classified as mild moderate or severe, insertion time, total procedural time, total withdrawal time, inspection time (withdrawal time minus anytime suctioning, cleaning, and diagnostic biopsy or therapeutic procedure), and polypectomy time for each polyp removed. For each polyp, we will record the location, size, shape, and pathology.

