### Statistical Analysis and Sample Size:

- Normally distributed continuous variables will be summarized using means and standard deviations while non-normally distributed continuous variables will be summarized using medians and ranges.
- The primary endpoints for the study will be the inspection time and insertion time, , the total time per polypectomy, and the total procedure time.
- The secondary endpoints will be total time per polypectomy, total procedure times, and adenomas detected.
- All colonoscopies in the study will be performed by a qualified professional. Patients will be 40 and older and will be randomized to receive colonoscopy with or without the Endocuff. Data collected will include the type of scope used (adult versus pediatric), age, gender, indication, history of prior abdominal surgery and type, identification of diverticulosis (classified as mild moderate or severe), insertion time, total procedural time, total withdrawal time, inspection time (withdrawal time minus anytime suctioning, cleaning, and diagnostic biopsy or therapeutic procedure), and polypectomy time for each polyp removed. For each polyp, we will record the location, size, shape, and pathology.

There will be a sample size of 200 subjects enrolled in this study. 100 randomized into two groups. With the sample size of 100 per group, the study will have 80% power to detect a 1 minute difference in the inspection time between the two groups. The inspection and insertion times will be compared using a two-sided two sample t-test, 5% significance level, and standard deviation of 2.5 minutes.

The data will be analyzed and the statistics performed by persons in the biostatistics department.

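### Operator-timed endpoints are to be compared with an unadjusted t-test, with no endoscopist identifier listed and no stratification described; if several endoscopists take part, cheap precision is forgone

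*Combined protocol and SAP*

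**What the plan says.** **Operator.** The Criteria section states that "All colonoscopies in the study will be performed by a qualified professional", and the Statistical Analysis and Sample Size section repeats this. Neither gives the number of operators, their experience or how they are assigned to cases.

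**Data list.** The same two sections list what will be collected: scope type, age, gender, indication, prior abdominal surgery, diverticulosis grade, the several times, and details of each polyp. Endoscopist is in neither list. Scope enters as the "type of scope used (adult versus pediatric"). Neither section says when it is chosen.

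**Randomisation.** Of the subjects, the Methods section says "They will be randomized to one of two arms", and it names the arms. It describes no stratification, blocking or concealment.

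**Analysis.** "The inspection and insertion times will be compared using a two-sided two sample t-test". No covariate model appears anywhere. The sample-size paragraph claims that "the study will have 80% power to detect a 1 minute difference in the inspection time between the two groups", based on 100 subjects per group and a "standard deviation of 2.5 minutes". It does not say whether that figure is a total or a within-endoscopist standard deviation.

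**The concern.** Insertion time, inspection time, time per polypectomy and total procedure time all depend on who holds the scope. If several endoscopists contribute, differences between them are part of the spread of these times, and an unadjusted t-test leaves that part in the error term. Recording the operator and putting the operator in the model would remove it without further patients. If the identifier is not collected, the study dataset cannot support this later.

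Scope type raises a smaller, separate question. The text does not say that the adult or pediatric scope is chosen before the arm is known. If the choice did respond to the arm, the two groups could differ in scope as well as in cuff. The scope actually used would then be a post-randomisation variable, and adjusting for it would not be a safe repair.

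**Working it through.** **Inputs from the Statistical Analysis and Sample Size section:** difference 1 minute, standard deviation 2.5 minutes, 100 per group, two-sided 5% level.

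**Input assumed:** the share r of inspection-time variance explained by endoscopist. The documents give no between-operator variance, so r is shown at 10%, 20% and 30%, with more than one operator.

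**Step 1. The plan's own figure.** The standard error of the difference is 2.5 × √(2/100) = 0.354 minutes. The noncentrality is 1/0.354 = 2.83. With 198 degrees of freedom the critical value is 1.972, and the noncentral t distribution gives power 80.4%. The stated 80% is reproduced.

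**Step 2. Adjusting for endoscopist, if 2.5 is the total standard deviation.** The residual standard deviation is 2.5 × √(1 − r), and the noncentrality is 1/(residual SD × √(2/100)).

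| r (assumed) | Residual SD (min) | Noncentrality | Power, 100 per group |
|---|---|---|---|
| 0 (planned test) | 2.50 | 2.83 | 80.4% |
| 10% | 2.37 | 2.98 | 84.3% |
| 20% | 2.24 | 3.16 | 88.2% |
| 30% | 2.09 | 3.38 | 92.0% |

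The gain is 3.9, 7.8 or 11.6 percentage points. These figures treat operators as balanced across arms. Spending five degrees of freedom on operator terms (193 instead of 198) changes none of them in the first decimal.

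**Step 3. The other reading of 2.5.** If 2.5 were a within-endoscopist standard deviation, the total would be 2.5/√(1 − r), that is 2.64, 2.80 or 2.99 minutes. The planned unadjusted test would then have 76.1%, 71.1% or 65.4% power. The documents do not settle which reading applies.

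**Step 4. Chance imbalance between operators.** Suppose two operators each do half the cases and allocation is unstratified. The standard deviation of the arm difference in one operator's share is √(2 × 0.25/100) = 0.071, so the 95% range is 1.96 × 0.071 = ±0.14, or about 14 percentage points. An assumed 1-minute gap between the operators would shift the arm difference by up to about ±0.14 minutes; a 2-minute gap by about ±0.28. This is chance variation that the t-test already allows for, not bias.

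**Step 5. Why stratification needs the model as well.** Stratifying by endoscopist but keeping the plain t-test makes the test conservative. Its true type I error is about 2 × (1 − Φ(1.96/√(1 − r))), which is 3.9%, 2.8% or 1.9% for the three values of r.

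**Step 6. Scope type, as an illustration only.** Any shift equals the arm difference in scope mix times the effect of scope on time. Assuming a 20-point difference and an effect of 1 to 2 minutes, it is 0.20 × 1 = 0.2 to 0.20 × 2 = 0.4 minutes. Neither factor comes from the documents.

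**The case against.** The strongest reply is that nothing here is an error. Subjects are individually randomised, so the t-test is valid whether or not operators differ, and the planned power is reached. That stands. A reader might infer that operator variance lowers the stated power. With 2.5 minutes as the total standard deviation it does not, because that variance is already inside the figure; what is lost is a possible gain. A shortfall arises only under the within-endoscopist reading, which the documents neither state nor exclude.

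The number of operators is unknown, and with one operator the endoscopist part disappears. That stands too. A reader might also infer that endoscopist will not be recorded, or that randomisation will not be stratified. The data list is introduced in terms that do not make it exhaustive, and the randomisation method is not described at all. The supportable statement is that these items are unlisted and undescribed. Even so, the one analysis that is stated makes no use of the operator.

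On scope, a reader might infer that its choice depends on the arm and biases the comparison. No section says that scope is chosen after allocation, or that the cuff favours one type. The Introduction says of the cuff "The device comes in several sizes and can fit the tips of most commonly used colonoscopes", which if anything weakens the idea. A change of scope prompted by the cuff could also be regarded as part of the effect of using the cuff, depending on what the trial means to estimate. Because scope used is recorded, a difference between arms would at least be visible.

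Finally, stratified blocks carry a risk of their own. Operators see whether a cuff is fitted, so with fixed blocks each could follow the sequence and predict coming allocations. The fix has to allow for this.

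**Conclusion.** The point holds as a cheap improvement, not as a flaw that invalidates the comparison. For endpoints that depend on the operator, the plan lists no endoscopist identifier, describes no stratification and states an unadjusted test. If more than one endoscopist takes part and 2.5 minutes is the total standard deviation, adjustment would raise power from 80.4% to between 84.3% and 92.0% at the same sample size, for an assumed variance share of 10% to 30%. The size of the gain rests wholly on that assumed share; what the text omits does not. The documents do not support a claim of bias from the operator or of an error in the stated power, and the scope concern is only a possibility worth closing off.

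**What to change.** 1. State how many endoscopists will take part, and add a coded endoscopist identifier to the data list in both sections where it appears.
2. If there is more than one, stratify randomisation by endoscopist, with allocation concealed and block sizes varying at random. Replace the two-sample t-test with a linear model containing arm and endoscopist.
3. Record the intended scope type (adult or pediatric) before the allocation is opened, and use that, not the scope used, as a covariate.
4. State whether the 2.5-minute standard deviation is total or within endoscopist. If it is total, the 200 subjects need not change.

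With a single operator, say so; of the design and analysis changes, only the scope step then applies.

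The cost is one extra data field for the endoscopist, a note of the intended scope before allocation, and slightly more work in setting up randomisation. No further subjects are needed under the total reading.

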### **Inclusion criteria**

- Referral for screening or surveillance colonoscopy
- Ability to provide informed consent
- 40 years and older

### **Exclusion criteria**

- Prior history of colon cancer
- History of inflammatory bowel disease
- Prior surgical resection of any part of the colon
- Use of anti-platelet agents or anticoagulants that precludes the removal of polyps during the procedure
- History of polyposis syndrome or HNPCC
- Inability to give informed consent
- Family history of colon cancer in a first degree relative < 60 years or two first degree relatives with colorectal cancer

### Statistical Analysis and Sample Size:

- Normally distributed continuous variables will be summarized using means and standard deviations while non-normally distributed continuous variables will be summarized using medians and ranges.
- The primary endpoints for the study will be the inspection time and insertion time, , the total time per polypectomy, and the total procedure time.
- The secondary endpoints will be total time per polypectomy, total procedure times, and adenomas detected.
- All colonoscopies in the study will be performed by a qualified professional. Patients will be 40 and older and will be randomized to receive colonoscopy with or without the Endocuff. Data collected will include the type of scope used (adult versus pediatric), age, gender, indication, history of prior abdominal surgery and type, identification of diverticulosis (classified as mild moderate or severe), insertion time, total procedural time, total withdrawal time, inspection time (withdrawal time minus anytime suctioning, cleaning, and diagnostic biopsy or therapeutic procedure), and polypectomy time for each polyp removed. For each polyp, we will record the location, size, shape, and pathology.

There will be a sample size of 200 subjects enrolled in this study. 100 randomized into two groups. With the sample size of 100 per group, the study will have 80% power to detect a 1 minute difference in the inspection time between the two groups. The inspection and insertion times will be compared using a two-sided two sample t-test, 5% significance level, and standard deviation of 2.5 minutes.

The data will be analyzed and the statistics performed by persons in the biostatistics department.

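### The plan names one primary endpoint in one section and four in another, lists two of the four as secondary as well, and gives no rule for combining them, so its 5% and 80% hold at trial level only if inspection time is the sole primary

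*Combined protocol and SAP*

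**What the plan says.** Three sections of the combined protocol and SAP define the primary comparison, and they disagree.

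- **Primary End-point** gives one measure: "The inspection time will be shorter because the proximal sides of the folds are more quickly exposed with Endocuff Vision". Part of the reason it offers, tip stability during loop withdrawal, is the reason the Introduction gives for faster insertion: "Endocuff Vision could improve insertion because during loop withdrawal the cuff tends to stabilize the position of the tip".
- **Objectives** gives four measures under the primary objectives: "To compare the insertion time, inspection time, the total time per polypectomy, and the total procedure time".
- **Statistical Analysis and Sample Size** calls the same four measures primary endpoints: "The primary endpoints for the study will be the inspection time and insertion time, , the total time per polypectomy", followed by total procedure time. The next bullet then reads "The secondary endpoints will be total time per polypectomy, total procedure times, and adenomas detected", so two measures carry both labels.

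The inferential detail covers only part of the list. The test and level are given for two measures: "The inspection and insertion times will be compared using a two-sided two sample t-test, 5% significance level". Power is given for one: "the study will have 80% power to detect a 1 minute difference in the inspection time between the two groups". Time per polypectomy and total procedure time have no stated test or significance level. Nowhere is there a multiplicity adjustment, an order of testing, or a statement of whether one or all of the primaries must be significant.

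**The concern.** The primary endpoint fixes what the trial may conclude. Here a report written after the data are seen could present one or four measures as primary and cite a section for either choice. It could also present two, by dropping the measures that are also called secondary and relying on the t-test sentence.

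The error rate and power of the trial as a whole depend on which set applies and on the success rule. If any one significant primary is enough, the chance of a false positive claim exceeds 5%. If all must be significant, error is controlled but the chance of success is below 80%. A fixed sequence starting with inspection time would preserve both figures for that endpoint, but none is stated.

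**Working it through.** **Inputs from Statistical Analysis and Sample Size:** 100 per group, difference 1 minute, SD 2.5 minutes, two-sided two-sample t-test at 5%.

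**Step 1. The plan's own figure (inspection time alone).** Noncentrality = 1 / (2.5 × √(2/100)) = 2.828, with 198 degrees of freedom and critical value 1.972. Exact noncentral-t power is 80.4% (normal approximation 80.7%), and the smallest n reaching 80% is 100 per group. The stated 80% is reproduced.

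**Step 2. Any one significant primary counts, each tested at 5%.** For k independent tests, family-wise error = 1 − 0.95^k:

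- k = 2: 1 − 0.95² = 9.75%
- k = 4: 1 − 0.95⁴ = 18.5%

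The documents give no correlations between the times. The table assumes jointly normal test statistics with a common correlation r. For k = 4 it also assumes 5% tests for the two measures with no stated level.

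| r | two primaries | four primaries |
|---|---|---|
| 0 | 9.75% | 18.5% |
| 0.3 | 9.5% | 17.4% |
| 0.5 | 9.1% | 15.6% |
| 0.7 | 8.3% | 13.0% |
| 0.9 | 7.0% | 9.4% |

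Full independence of all four is implausible, because total procedure time presumably includes time spent on the others. As an illustration only, three independent equal-variance times plus their sum give 16.1%.

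**Step 3. All primaries must be significant.** Error stays at or below 5%. Joint power is computed assuming that every measure has the standardised effect planned for inspection time (1/2.5 = 0.4) and 100 analysable subjects per group, so each has marginal power 0.8036. With independence it is 0.8036² = 64.6% for two and 0.8036⁴ = 41.7% for four.

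| r | two primaries | four primaries |
|---|---|---|
| 0 | 64.6% | 41.7% |
| 0.3 | 67.2% | 50.4% |
| 0.5 | 69.2% | 56.2% |
| 0.8 | 73.4% | 66.2% |

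The four-primary column is optimistic. The Criteria section records "inspection time (withdrawal time minus anytime suctioning, cleaning, and diagnostic biopsy or therapeutic procedure), and polypectomy time for each polyp removed", so polypectomy time exists only for subjects who had a polyp removed, and fewer than 100 per group would contribute.

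**Step 4. Splitting alpha.** The calculation of Step 1 is repeated for inspection time at reduced levels.

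| Level for inspection time | Power at 100 per group | n per group for 80% | Extra subjects |
|---|---|---|---|
| 0.05 (single primary, or first in a fixed sequence) | 80.4% | 100 | 0 |
| 0.04 (unequal split) | 77.6% | 106 | 2 × 6 = 12 |
| 0.025 (Bonferroni, two) | 71.5% | 121 | 2 × 21 = 42 |
| 0.0125 (Bonferroni, four) | 62.1% | 141 | 2 × 41 = 82 |

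**The case against.** The strongest reply is that the documents already point to one design. The section headed Primary End-point names inspection time only, the sole power statement is for inspection time, and 100 per group is exactly the smallest size giving 80% for that endpoint tested alone. On that reading nothing numerical is wrong.

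This is a fair account of the probable intent, but it does not settle the matter. The section that governs the analysis lists four primary endpoints in so many words, in agreement with the primary objectives, and nothing says which section prevails.

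Some narrower points do stand:

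- The two-primary set is an inference; no section states it. The conflict between one and four, and the double labelling, do not depend on it.
- The Objectives section lists objectives, not endpoints, so only the statistics section names four primary endpoints outright.
- The 5% level is stated only for inspection and insertion time, so the inflation that rests on stated levels is the two-test figure. The four-test figures need an added assumption.
- Total procedure time is listed but not defined, and time per polypectomy is a per-polyp quantity, so the sum model in Step 2 does not represent the listed endpoints.
- A fixed sequence is free for inspection time only. Under the assumptions of Step 3, the second endpoint in the sequence would be claimed with probability of about 65% to 73%, not 80%.
- Choosing inspection time as the primary is a recommendation. The Introduction puts insertion first among the expected benefits.

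**Conclusion.** The contradiction is in the current text and no reading removes it: one primary endpoint in one section, four in another, and two of the four also secondary. The sample-size arithmetic is correct for inspection time alone. It cannot be carried over to two or four primaries, because the rule that would determine error and power is absent.

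Under an any-one rule the excess over 5% remains at every correlation examined. Under an all-must-be-met rule power falls short of 80% at every correlation examined, by roughly 7 to 15 percentage points for two primaries and 14 to 38 for four. The direction does not depend on the assumed correlations. The sizes do, and they also rest on equal standardised effects for the power figures and on assumed 5% tests for the two measures without a stated level. Because this concerns the trial's main claim, it should be resolved before any analysis.

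**What to change.** Make inspection time the single primary endpoint at two-sided 5%, in the same words in Objectives, Primary End-point, and Statistical Analysis and Sample Size. List insertion time, time per polypectomy and total procedure time as secondary only. Either test them in a stated fixed sequence after inspection time, or report them as estimates with 95% confidence intervals. The total stays at 200 and the 80% stands. The cost is protocol wording, with no extra subjects or data. The downside is that three times lose primary status, though a fixed sequence still allows formal tests of them if inspection time is significant.

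If the sponsor prefers several primaries, state the set, the success rule, and the test and level for each measure, and restate the power:

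- A fixed sequence starting with inspection time adds no subjects and keeps 5% overall and 80% for that endpoint; later endpoints have less.
- An all-must-be-met rule needs a joint-power statement with its assumed effects and correlations.
- An equal Bonferroni split needs 42 (two primaries) or 82 (four primaries) more subjects in total to keep 80% for inspection time. Giving inspection time 0.04 needs 12 more, or leaves 77.6% at the present size.

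### Does the missing landmark between insertion and withdrawal, with loop removal cited under both phases, undermine the inspection-time comparison?

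*Combined protocol and SAP*

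**What the plan says.** The Criteria section lists the times to be recorded, "insertion time, total procedural time, total withdrawal time, inspection time", and the Statistical Analysis and Sample Size section repeats the list. Only inspection time has a formula, the same in both places: "inspection time (withdrawal time minus anytime suctioning, cleaning, and diagnostic biopsy or therapeutic procedure". Insertion time and total withdrawal time are named without a start or an end.

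The Introduction gives each phase its own mechanism. For the first phase, "Endocuff Vision could improve insertion because during loop withdrawal the cuff tends to stabilize the position of the tip". For the second, "Similarly, during inspection, the main goal is to evaluate the proximal sides of folds and flexures". The Primary End-point section opens with the same inspection mechanism, "The inspection time will be shorter because the proximal sides of the folds are more quickly exposed with Endocuff Vision", but then adds the device's ability to "stabilize the position of the colonoscope tip during loop withdrawal, thus preventing its backward movement and speeding loop removal".

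The Statistical Analysis and Sample Size section names both times among the primary endpoints. It states that "the study will have 80% power to detect a 1 minute difference in the inspection time between the two groups", with 100 per group and an SD of 2.5 minutes, and that "The inspection and insertion times will be compared using a two-sided two sample t-test" at the 5% level. Completion of insertion is not a listed data item, and no rule covers the times from an incomplete examination.

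**The concern.** Inspection time is withdrawal time less certain activities, so an undefined withdrawal time leaves the powered outcome with an undefined input. The formula does not subtract loop removal, so any loop removal after the withdrawal clock starts counts as inspection. With the two sections naming different phases for loop removal, a reader may ask whether the planned one-minute saving includes it.

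The clock points are fixed during the procedure, no section says who does the timing or mentions blinding, and biostatisticians cannot rebuild them later. If operators stopped the insertion clock at a different point when the cuff was in use, time would move from one primary endpoint to another in one arm only.

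The formula also does not require a completed insertion, so read literally a partial examination counts as a short inspection. If such cases were more common without the cuff, the control mean would fall and the device's benefit would be understated.

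**Working it through.** **Inputs from the plan** (Statistical Analysis and Sample Size): 100 per group, SD 2.5 minutes, difference 1 minute, two-sided t-test at 5%. Every other input below is an assumption, because the documents give no timing error, clock shift, mean time or rate of incomplete insertion.

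**1. The plan's own figure.** Standard error = 2.5 × √(2/100) = 0.354 minute. Power for 1 minute from the noncentral t is 80.4%, so the stated 80% reproduces.

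**2. Unclear landmark, same practice in both arms.** A fixed offset e added to every subject's time cancels: (device mean + e) − (control mean + e) = device mean − control mean. Random error with SD s inflates the SD to √(2.5² + s²):

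| Assumed s (min) | Total SD (min) | Power for 1 min |
|---|---|---|
| 0.25 | 2.512 | 80% |
| 0.5 | 2.550 | 79% |
| 1.0 | 2.693 | 74% |

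**3. Clock shifted in one arm only, no true effect.** Rejection is 5.9% for an assumed shift of 0.10 minute, 10.8% for 0.25 and 29.1% for 0.50. These are serious, but they describe differential timing, which no section suggests.

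**4. Part of the planned minute is loop removal timed as insertion.** If 0.10, 0.25 or 0.50 minute is, inspection shows 0.90, 0.75 or 0.50 minute, with power 72%, 56% or 29%. This redefines the effect on inspection. The saving is not lost: it appears in insertion time, which is also primary and has its own t-test.

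**5. Incomplete insertions kept in the inspection analysis.** Assume 5% in control and 2% with the device, a mean of 8 minutes, and incomplete cases recorded at a fraction k of the usual time.

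- No true effect: bias = (0.05 − 0.02) × 8 × (1 − k), which is 0.168, 0.120 or 0.072 minute at k = 0.3, 0.5 or 0.7. Simulation (20,000 trials per scenario) gives rejection of 7.0%, 6.2% and 5.3%.
- True difference −1 (device mean 7): observed difference = −1 + 0.05 × 8 × (1 − k) − 0.02 × 7 × (1 − k), which is −0.82, −0.87 or −0.92. Simulated power is 58%, 67% and 73%.
- Equal rates, 5% in each arm, no true effect: no bias.

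**6. The analysis change that could be considered: t-tests on completed insertions only, with incomplete cases ranked worst in a sensitivity test.** Same assumed rates.

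- Insertion, no true effect: residual bias is 0, 0.07 or 0.15 minute at correlation 0, 0.5 or 1 between failure and time, with rejection 4.9%, 5.4% or 7.3%.
- Inspection, true −1: the estimate is −1.00 at correlation 0 and −0.93 at 0.5, with power 79% and 74%.
- Worst-rank Wilcoxon, no effect on time, failure unrelated to speed: rejection is 6.6%, rising to 10.1% if 10% of control and 4.6% of device insertions fail.
- Worst-rank Wilcoxon, true −1, with the rates reversed (5% device, 2% control): power is 59%, against 79% for the t-test.

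**The case for a change.** The strongest argument for acting is that this gap sits in the powered outcome, cannot be repaired after the procedure, and would cost only a few sentences and a yes/no field to close. Operators can see which arm they are in, so a one-sided shift cannot be ruled out, and half a minute in one arm would raise the false-positive rate to 29%. Without a landmark, a published one-minute saving would also be harder to interpret.

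The absence of a landmark stands, as does the mismatch between the Introduction and the Primary End-point section. The inference to a biased comparison does not. The mismatch is between two statements of rationale. Neither allocates minutes, and the formula that does is identical wherever it appears; the loop-removal clause reads as wording carried over from the Introduction. Investigators timing both phases of the same procedure would be expected to use a common dividing point in both arms, and a written definition that leaves the landmark for the sponsor to fill in records that practice without altering the analysis.

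On incomplete insertions, the list of data need not be exhaustive, and the possible harm rests on rates the documents do not give. Its direction is not fixed either. It understates the device's benefit when inspections are cut short; if failed insertions were instead kept at long attempt times and were more common in control, the insertion comparison would move in the device's favour.

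**Conclusion.** The plan leaves a definition unstated and repeats a rationale in the wrong place; it does not contain a demonstrated bias, and no change follows.

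For the landmark, a common offset cancels and random error up to an SD of 1.0 minute leaves power at 74% or more. The larger figures (29% false rejection, 29% power) need, respectively, a half-minute shift confined to one arm and half the planned effect moved into another primary endpoint.

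For incomplete insertions, completed-only tests are a trade-off without clear gain. They drop subjects on a post-randomisation outcome the device may affect. Their residual bias, 0.07 to 0.15 minute when failure is related to time, overlaps the 0.07 to 0.17 minute they would remove, and the worst-rank companion test can reject 10.1% of the time with no effect on time.

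This rests on both arms being timed the same way and on incomplete insertions being about as common in each. The documents state neither and contradict neither. Evidence that timing practice or completion differed by arm would reopen the question.
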